9.2.2. Method used to detect adverse events and SAEs

Care will be taken not to introduce bias when detecting AE and/or SAE. Open-ended and non-leading verbal questioning of the participant is the preferred method to inquire about AE occurrence.

9.2.3. Follow up on adverse events and SAEs

After the initial AE/SAE report, the investigator is required to proactively follow each participant at subsequent visits/contacts. All SAEs will be followed until the event is resolved, stabilized, otherwise explained, or the participant is lost to follow-up (as defined in Section 8.3). Further information on follow-up procedures is given in Appendix 4.

9.2.4. Regulatory requirements of SAE reporting

- Prompt notification by the investigator to the sponsor of a SAE is essential so that legal obligations and ethical responsibilities towards the safety of participants and the safety of a study treatment under clinical investigation are met.

- The sponsor has a legal responsibility to notify both the local regulatory authority and other regulatory agencies about the safety of a study treatment under clinical investigation. The sponsor will comply with country-specific regulatory requirements relating to safety reporting to the regulatory authority, Institutional Review Boards (IRB)/Independent Ethics Committees (IEC), and investigators.
- Investigator safety reports must be prepared for suspected unexpected serious adverse reactions (SUSAR) according to local regulatory requirements and sponsor policy and forwarded to investigators as necessary.
- An investigator who receives an investigator safety report describing a SAE or other specific safety information (eg, summary or listing of SAE) from the sponsor will review and then file it along with the Investigator's Brochure and will notify the IRB/IEC, if appropriate according to local requirements.

9.2.5. Cardiovascular events and death

For any cardiovascular events detailed in Appendix 4 and all deaths, whether or not they are considered SAEs, specific Cardiovascular (CV) and Death sections of the CRF will be required to be completed. These sections include questions regarding cardiovascular (including sudden cardiac death) and non-cardiovascular death.

The CV CRFs are presented as queries in response to reporting of certain CV MedDRA terms. The CV information should be recorded in the specific cardiovascular section of the CRF within one week of receipt of a CV Event data query prompting its completion.

The Death CRF is provided immediately after the occurrence or outcome of death is reported. Initial and follow-up reports regarding death must be completed within one week of when the death is reported.

9.2.6. Pregnancy

- Details of all pregnancies in female partners of male participants will be collected after the start of study treatment and until Final Visit.
- If a pregnancy is reported, the investigator should inform GSK within 24 hours of learning of the pregnancy and should follow the procedures outlined in Appendix [X].
- Abnormal pregnancy outcomes (eg, spontaneous abortion, fetal death, stillbirth, congenital anomalies, ectopic pregnancy) are considered SAE.

9.3. Management of overdose

A dosage of the product exceeding 400 units within 24 hours shall be considered as overdose in this study. Overdose may cause excessive pharmacodynamic responses such as hyposthenia, muscular paralysis, and other localized adverse reactions. Symptoms and signs may not immediately appear following dose. Moreover, blepharoptosis, dysarthria, dysphagia, dyspnea, myasthenia, and other events suspected to be an effect on other muscles distal to the treated muscle have been reported overseas. If such a symptom appears, the subject should be carefully monitored, and given appropriate interventions, if necessary with hospitalization. Also, supportive therapies such as artificial breathing should be considered for respiratory symptoms.

Upon confirmation of overdosage, the investigator should;

1. Contact the Medical Monitor immediately.

Carefully monitor the adverse event/SAE, and laboratory abnormalities in the subject for at least 4 weeks; and

Document the quantity of the excess dose as well as the duration of the overdosing in the CRF.

The investigator shall discuss with the sponsor's medical monitor on the clinical assessment of the subject, and upon which, decide whether or not to discontinue the study treatment.

9.4. Safety assessments

Assessment timepoints for all safety parameters are as shown in SoA.

9.4.1. Physical examination

Physical examination (complete version): Only during screening

- The head and neck, skin, lungs, cardiovascular system, abdominal region (liver and spleen), gastrointestinal system, lymph node, and nervous system should be examined, and the results thereof should be recorded; these organs should be examined for the presence/absence of pre-existing conditions and abnormal findings, and if there is any suspected abnormality, detailed examinations should be performed.
- The pulmonary function test should be conducted in details if any sign of pulmonary impairment is found. For the pulmonary function test, spirometry by pulmonologists is recommended.

Physical examination (simplified version): To be conducted only if an eligibility criterion is not met during the open-label period.

- At least, the lungs, cardiovascular system, and abdominal region (liver and spleen) should be examined, and the results thereof should be recorded.
- The investigator should pay attention to clinical signs and symptoms related to a history of serious disease.

The physical examinations should be performed by doctors in accordance with the standard clinical guidelines of each study site.

9.4.2. Vital signs

- For the vital signs, body temperatures (oral, intra-aural, or axillary fossa), systolic/diastolic blood pressures, and pulse rates should be measured in a semi-recumbent position after a 5-minute rest. If measurement in a semi-recumbent position is difficult, measurement in another position (e.g., sitting) is acceptable. In this case, however, the measurement should be performed always in the same position during the study period.
- If a temperature is to be measured orally, the subject must refrain from eating food or drinking beverage within 5 minutes before the measurement. The method for the measurement of body temperature must remain the same throughout the study.

- The blood pressures and pulse rates should be measured with an automated device. A manual method may be used only if there is no automated device available for use.

9.4.3. Height and weight

The standard clinical guidelines of each study site should be followed.

9.4.4. Pulmonary test

- Refer to SoA for the timepoints and frequency of testing.
- If post-injection SpO₂ is decreased by 3% or more from the baseline (pre-injection on Day 1) or a SpO₂ value is <95%, medical examination by pulmonologist is required. A subject with pulmonary dysfunction due to study treatment based on the investigator's opinion will be referred to a pulmonologist as well.
- If a medical institution has no pulmonologist, visit other hospitals for medical examination by specialists. For the pulmonary function test, spirometry by pulmonologists is recommended.
- If a subject is referred to a pulmonologist and considered to have no concerns about pulmonary function, the investigator should carefully consider whether to start or continue study treatment.

9.4.5. ECG

- QTc should be determined based on a single measurement of ECG or the mean of ECG measured at 3 timepoints in a short period of time (e.g., 5 to 10 minutes).
- An automated measurement and manual re-interpretation in accordance with SoA should be used to collect data on the heart rates, PR, QRS, QT, and QTc interval. Refer to section [8.2.2.](#) for QTc-related treatment discontinuation standard, and additional QTc to be measured as required.
- Each interval between timepoints for the measurement of ECG should be minimized as much possible (within 2 minutes). The measurement of ECG should be performed 3 times consecutively and completed within 5 to 10 minutes.

9.4.6. Neutralizing antibody test

The investigator shall draw blood for neutralizing antibody samples in accordance with the study schedule. The neutralizing antibody will be measured collectively by central laboratories designated by GSK (Intertek Pharmaceutical Services Co. and Pacific BioLabs Co.). The screening samples will be retained temporarily by the central laboratories, and then, upon retrieval of samples from all subjects, will be collected and tested by Intertek for screening. Samples tested positive at Intertek will be separately sent to Pacific BioLabs for retest to finalize the results of neutralizing antibody test. The above procedures shall also be taken for samples collected for Week 12 visit during the blinded period, and upon completion of study treatment in all subjects.

9.4.7. Clinical Safety Laboratory Assessments

- Refer to Appendix 2 for the list of clinical laboratory parameters that should be tested, and to SoA for the timepoints and frequency of testing.
- The investigator must review the laboratory report, document this review, and record any clinically relevant changes occurring during the study in the AE section of the CRF. The laboratory reports must be filed with the source documents. Clinically significant abnormal laboratory findings are those which are not associated with the underlying disease, unless judged by the investigator to be more severe than expected for the participant's condition.
- All laboratory tests with values considered clinically significantly abnormal during participation in the study should be repeated until the values return to normal or baseline or are no longer considered significantly
- If such values do not return to normal/baseline within a period of time judged reasonable by the investigator, the etiology should be identified and the sponsor notified.
- All protocol-required laboratory assessments, as defined in Appendix 2, must be conducted in accordance with the laboratory manual and the SoA.
- If a result of clinical laboratory test not scheduled in the protocol is obtained by a study site, which requires a change in the patient management, or is determined to be clinically important by the investigator, that is SAE, adverse event, an event requiring dose modification, or any other relevant event, the record thereof must be documented in the CRF.
- Follow-up investigation may be performed at any time during the study as determined to be necessary by the investigator, or required by the Japanese regulation.

9.5. Pharmacokinetics

PK parameters are not evaluated in this study.

9.6. Pharmacodynamics

Pharmacodynamic parameters are not evaluated in this study.

9.7. Genetics/Pharmacogenetics

Genetics and pharmacogenetics are not evaluated in this study.

9.8. Biomarkers

Biomarkers are not evaluated in this study.

9.9. Pharmacoeconomics

Pharmacoeconomic parameters are not evaluated in this study.

10. STATISTICAL CONSIDERATIONS

10.1. Sample Size Determination

This study is not intended to verify a statistical hypothesis, but is rather intended to verify that the responder rate in the 400 units group exceeds that in the 240 units group, and for which, about 120 subjects (60 in each treatment group) are to be enrolled.

During Treatment Period 1 of this study, 160 units of the product will be administered in the muscle which affects the elbow; thus, the sample size was determined in reference to an overseas phase III study (Study 127) in which a similar dosage as this study (150 units) was administered in the muscle which affects the elbow. The responder rate in the elbow at Week 6 of the initial dose in Study 127 was 72.2% and 47.1% in the product 300 units group (150 units in the muscle which affects the elbow flexors) and placebo group, respectively. The number of subjects in the intention-to-treat (ITT) population was small in both the product 300 units group and placebo group of Study 127, which was 18 subjects each; thus, considering the uncertainty of the results of Study 127, the responder rates in the product 400 units and 240 units groups in this study were conservatively assumed to be 70.0% and 50.0%, respectively. Assuming that the sample size is 60 subjects in each group, the power of test to detect an intergroup difference in the responder rates would be about 62% with a two-sided significance level of 5% while the probability of the responder rate in the product 400 units group to exceed that in the product 240 units group as a point-estimate would be $\geq 98\%$.

With about 120 subjects enrolled, 100 subjects are expected to complete Week 48 of the initial dose.

10.2. Populations for Analyses

Populations for statistical analyses in this study are defined as follows.

Population	Description
ITT	All subjects randomized in the study and had at least 1 post-baseline efficacy assessment: ITT is the primary efficacy analysis population, and the subjects will be analyzed in line with the randomized treatment group.
Safety	All subjects randomized in the study and received study treatment at least once: The subjects will be analyzed based on the treatment actually given.

10.3. Statistical Analyses

10.3.1. Efficacy Analyses

This study is not intended to verify a statistical hypothesis; thus, there will be no statistical test.

All of the efficacy analyses will be performed on the ITT population separately for the blinded period and the open-label period.

Endpoints	Statistical Analysis Methods
Primary	
The primary endpoint is the proportion of subjects whose MAS score on the elbow at Week 6 of the initial dose decreased by at least 1 level from the baseline (responder rate). The primary endpoint will be calculated as the proportion of subjects whose MAS score decreased by at least 1 level from the baseline in the ITT population. Also, a 95% confidence interval of the intergroup difference in the responder rate will be computed. Subjects with no MAS score available at Week 6 will not be counted as subjects whose MAS score decreased by at least 1 level from the baseline (that is, counted in as non-responder).
 
The MAS scores, 0, 1, 1+, 2, 3, and 4 will be encoded to 0, 1, 2, 3, 4, and 5, respectively, for the analysis purpose.

Secondary	
Unless specified otherwise, the data up to Week 12 of treatment will be summarized for each repeated dose during the open-label period.
 
During the blinded period, a mixed model for repeated measurement (MMRM) will be used for the analysis on the endpoints specified below, and the least-square mean and 95% confidence interval will be calculated. The details of the model will be described in the statistical analysis plan. For the open-label period, only a summary statistics will be performed for each treatment group. Missing values will not be imputed.
 
 · Change in MAS score in the fingers, thumb, wrist, and elbow from the baseline · Change in Disability Assessment Scale (primary endpoint) from the baseline 
The proportion of subjects in whom MAS score in the fingers, thumb, wrist, and elbow decreased by at least 1 level from the baseline (responder rate) during the blinded period will be analyzed with the same method as that for the primary endpoint. For the open-label period, the denominator to be used for the calculation of responder rate shall be the number of subjects in each subgroup stratified by the number of injections given, not the ITT population. Also, a 95% confidence interval of the intergroup difference in the responder rate will not be calculated.

Exploratory	
Time to patient-reported onset of spasticity symptom relief will be evaluated for subjects who reported alleviation of spasticity at in 2 weeks postdose. The number of days from dose to the alleviation of spasticity will be summarized for each treatment group.
 
Clinical Global Impression of Change (CGI) assessed by an investigator, CGI assessed by a patient, and Patient-reported benefit of injection will be summarized for each treatment group. Missing values will not be complemented.
 
Other details will be specified in the statistical analysis plan.

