5. STUDY DESIGN

5.1. Overall Design

This study is a 48-week multicenter, phase III study (a placebo controlled, randomized, double-blind comparative study and an open-label, uncontrolled study) to evaluate the efficacy and safety of the product in patients with post-stroke upper limb spasticity. The study period is up to 52 weeks, consisting of a screening phase up to 4 weeks, minimum 12-week blind phase (Part 1), maximum 36-week open-label phase (12 weeks per cycle with maximum 3 treatment periods, Part 2, Part 3 and Part 4). (Figure 5).

[figure not shown]

Figure 5 Study Design

In this study, the efficacy of 400 units of the product at Week 6 is evaluated, comparing to that of 240 units, and improvement tendencies are also evaluated in patients with post-stroke upper limb spasticity. The improvement will be defined as at least 1 reduction on the MAS score from baseline (a measurement value before injection of Day 1). The responder rate (the rate of the subjects that MAS score is reduced at least 1 from baseline) in the elbow flexors at Week 6 is set as an endpoint. As a point estimate, if the responder rate in the 400 units group outweighs that in the 240 units group, improvements tendencies will be considered to be positive.

For injection, use of the following any one of the tools: EMG, electrical stimulator, or ultrasonography, is recommended to ensure identification of the exact injection site. In the blind phase, use of at least one of the following tools: EMG, electrical stimulator, or ultrasonography, will be essential to ensure identification of the muscle to be injected correctly.

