7.3. Method of Treatment Assignment

After completion of all evaluations at screening phase/initiation of the blind phase, the subjects who met the inclusion criteria and none of the exclusion criteria will be given their randomization number at a case registry center and randomized to either the 240 or 400 units group. The assigned randomization number cannot be re-used. The table of the allocation will be prepared via a computer in GSK, using the RandAll systems.

Based on the MAS score (3 or 4) in the elbow flexors, subjects will be stratified at the time of randomization.

The subjects who meet the eligibility for the injections in the open-label phase can move forward to the open-label phase and be injected (Refer to section 5.1.3). In the open-label phase, 400 units of the product will be given to all subjects. Other detailed information will be described on SRM.

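### Randomisation is stratified by elbow MAS, but the primary analysis as written makes no use of the stratum: a minor loss of precision if the stratum predicts response

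*Protocol*

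**What the plan says.** Section 7.3 of the protocol sets the randomisation: "Based on the MAS score (3 or 4) in the elbow flexors, subjects will be stratified at the time of randomization". This is the only stratification factor it names.

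The primary row of section 10.3.1 fixes the endpoint (a drop of at least one MAS level at the elbow at Week 6), the population (ITT), the handling of a missing Week 6 score (non-responder) and the numerical coding of the scale. The responder rate is a proportion of the ITT population. On the comparison it says: "Also, a 95% confidence interval of the intergroup difference in the responder rate will be computed". It names no interval method and does not mention the stratum. The blinded-period responder rates at the other joints are to follow the same method.

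Section 10.3.1 sends the MMRM model to the SAP in so many words, and its exploratory row leaves other details there. The primary row contains no such deferral.

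Two further statements bear on how the interval is used. Section 10.3.1 opens with: "This study is not intended to verify a statistical hypothesis; thus, there will be no statistical test". Section 5.1 gives the criterion for a positive tendency: "As a point estimate, if the responder rate in the 400 units group outweighs that in the 240 units group", the tendency counts as positive.

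**The concern.** The stratification factor is the baseline of the endpoint itself. A patient starting at MAS 4 may well have a different chance of losing one level than a patient starting at MAS 3. If so, stratified randomisation removes part of the chance variation between the arms. An interval built from two overall proportions still counts that variation, so it comes out somewhat wider than it need be and covers slightly more than 95%.

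What is at stake is precision. With no test planned, this interval is the only stated measure of uncertainty for the primary comparison, and at 60 per arm it is already wide.

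**Working it through.** **Inputs, all from section 10.1.**
- Responder rates, which "were conservatively assumed to be 70.0% and 50.0%, respectively" (400 units first, then 240 units).
- Group size: 60 per arm.
- Stated power: about 62% at a two-sided 5% level.
- Stated probability that the 400-unit point estimate is the higher one: 98% or more.

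**1. Reproduce the plan's figures.**
- Unpooled SE = sqrt[(0.7×0.3 + 0.5×0.5)/60] = sqrt(0.46/60) = 0.08756.
- Pooled SE under no difference = sqrt(2×0.6×0.4/60) = 0.08944.
- Power, pooled = Φ[(0.20 − 1.96×0.08944)/0.08756] = 61.1%.
- Power, unpooled = Φ(0.20/0.08756 − 1.96) = 62.7%.
- Power by exact enumeration of the uncorrected chi-square test: 61.8%.
- Probability that the 400-unit rate exceeds the 240-unit rate: 98.9% by normal approximation, 98.5% exactly.

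Both of the plan's figures reproduce, so the planning inputs are a sound base for the next steps.

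**2. Unstratified interval.** Half-width = 1.96 × 0.08756 = 0.1716, or 17.2 percentage points.

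**3. Stratified interval.** Let w be the share of subjects with MAS 3 and g the responder-rate gap between the strata, taken as equal in both arms, with the strata balanced across arms. In an arm with overall rate p, the stratum rates are p + (1−w)g and p − wg. The within-stratum variance is p(1−p) − w(1−w)g². Summed over both arms:

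stratified variance = [0.46 − 2w(1−w)g²]/60.

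Example, w = 0.5 and g = 0.20: (0.46 − 0.02)/60 = 0.44/60. The SE ratio is sqrt(0.44/0.46) = 0.978 and the half-width is 16.8 points, about 0.4 point less.

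The protocol gives neither w nor g. The assumed ranges are w from 50% to 90% and g from 0 to 40 points.

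| Gap g (points) | Half-width, w = 50% | Half-width, w = 90% | Narrowing | Coverage of unstratified 95% CI |
|---|---|---|---|---|
| 0 | 17.2 | 17.2 | none | 95.0% |
| 10 | 17.1 | 17.1 | 0.2% to 0.5% | 95.0% to 95.1% |
| 20 | 16.8 | 17.0 | 0.8% to 2.2% | 95.2% to 95.5% |
| 30 | 16.3 | 16.9 | 1.8% to 5.0% | 95.4% to 96.1% |
| 40 | 15.6 | 16.6 | 3.2% to 9.1% | 95.7% to 96.9% |

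Coverage = 2Φ(1.96/SE ratio) − 1. An even split gives the largest gain, because w(1−w) is greatest there.

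**4. Gaps that differ between arms.** With even strata, the term removed becomes 0.25(g₁² + g₂²). Gaps of 20 and 30 points give sqrt(0.4275/0.46) = 0.964, which is 3.6% narrower. Gaps of 30 and 40 points give sqrt(0.3975/0.46) = 0.930, which is 7.0% narrower. Both lie within the range of the table.

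**The case against.** The strongest reply is that the protocol contains no error here. A reader might infer that it states a crude difference with a crude interval. It does not: neither word appears, no interval method is named, and a stratified interval in the SAP would not contradict section 10.3.1. Interval methods are commonly left to the SAP, which was not available for this review. This stands, and it limits the point to what the text does if followed as written. It does not remove the point, because the primary row defines the rate as an overall ITT proportion, settles its other details itself and, unlike the MMRM paragraph, defers nothing.

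A reader might also conclude that the interval is too wide as a matter of fact. The documents do not support that. They give no stratum shares and no stratum-specific rates, and the excess is nil if the stratum does not predict response.

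Nor can this be presented as lost power or as a threat to the trial's conclusion. No test is planned, and the rule in section 5.1 compares point estimates and ignores the interval. Chance imbalance in stratum size is not a strong argument either, since limiting it is what the stratified randomisation does. With exact balance, the weighted and unweighted differences coincide.

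Finally, whether the MMRM should contain the stratum is a question for the SAP, to which the protocol expressly sends that model, so it forms no part of this point.

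**Conclusion.** The point holds as a minor efficiency improvement. The design stratifies on the endpoint's own baseline, and the primary analysis, read as written, does not use that stratum. The unstratified interval is valid. At worst it is mildly conservative, and it is not biased by the omission.

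The size is conditional: from no gain to about 2% of a 17.2-point half-width for between-stratum gaps of up to 20 points, and up to 5% to 9% only for gaps of 30 to 40 points with evenly split strata. This rests on the planning rates, on strata balanced across arms, on equal gaps in both arms for the tabulated values, and on assumed shares and gaps.

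**What to change.** Before any unblinding, and so before the Week 24 data lock that section 10.3.4 allows, add to the primary row of 10.3.1 that the difference in responder rate and its 95% CI are Mantel-Haenszel weighted over the randomisation strata (elbow MAS 3 and 4). A stratified Newcombe interval or one based on the Sato variance would serve. Show the unadjusted responder rates by arm alongside. In section 5.1, say which of the two estimates, weighted or unadjusted, decides whether the tendency is positive. If the SAP already specifies the stratified interval, only the alignment of 10.3.1 and 5.1 remains.

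The cost is a few sentences and standard software. There are two small drawbacks. The weighted difference may not equal the difference between the displayed rates, which is why the rule in 5.1 must name one estimate. The MAS 4 stratum may also be sparse, in which case the stratified interval would rest on small cells.
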